# **3 OBJECTIVES AND ENDPOINTS**

OBJECTIVES	ENDPOINTS	JUSTIFICATION FOR ENDPOINTS
Primary		
To evaluate the acceptability, usability, appropriateness, and feasibility of PLANTS	In the follow-up survey, school staff will complete the following survey measures: - Acceptability of Intervention Measure - System Usability Scale - Intervention Appropriateness Measure - Feasibility of Intervention Measure	We use validated scales that assess high school staff's perceptions of the intervention's tolerability, user friendliness, fit, relevance, and successful execution.
Secondary		
To test the efficacy of PLANTS intervention for improving SGMY behaviors among high school staff	-Active empathic listening -Self-efficacy for supporting, affirming, and protecting SGMY -Self-efficacy of PLANTS change objectives -Positive bystander intervention behaviors	PLANTS is specifically designed to target these behavioral outcomes.

#### PLANTS Pilot Trial Version 1.0 Protocol STUDY21080178 2024.04.05 **OBJECTIVES ENDPOINTS** JUSTIFICATION FOR ENDPOINTS To assess PLANTS -PLANTS participation rate These measures assess school implementation -PLANTS completion rate staff's implementation and uptake of -Participation rate in live Zoom events the PLANTS intervention. To assess trial -Participation rate These measures assess the success implementation -Attrition rate of the pilot trial in reaching an -Intervention demand adequate number of school staff. To determine the -Parent backlash Although we anticipate the incidence safety of PLANTS -Social media backlash of these adverse events to be low. they are the most common and could -School board backlash be most harmful to school staff. -Suspension or removal from employment -Censorship of LGBTQ+ literature/history/stories or removal of books with LGBTQ+ representation from school libraries.

# 4 STUDY DESIGN

# 4.1 Overall Design

This is a two-armed cluster-randomized controlled pilot trial of the PLANTS intervention versus an active control group, EMAILS (E-learning to Maximize Academic Inclusion of LGBTQ+ Students). The single study site is the University of Pittsburgh. The primary objective is to assess the acceptability, usability, appropriateness, and feasibility of the PLANTS intervention. We hypothesize that high school staff will rate the PLANTS intervention as having high acceptability, usability, appropriateness, and feasibility in the follow-up survey.

The secondary objectives are to examine the extent to which the PLANTS course and trial successfully implemented and safe for high school staff and schools. We will also evaluate the extent to which, among high school staff participants in the PLANTS arm, they report pre-post improvements in active-empathic listening, self-efficacy for supporting, affirming, and protecting sexual and gender minority youths, and positive bystander intervention behaviors for bullying. We will also assess the extent to which, among high school staff, the PLANTS intervention is more efficacious in improving active-empathic listening, self-efficacy for supporting, and positive bystander intervention behaviors for bullying than an email intervention of publicly available resources. We hypothesize that participants in PLANTS will report greater active-empathic listening, greater self-efficacy for supporting, affirming, and protecting SGMY, and greater positive bystander intervention behaviors in the active control arm.

We will randomize schools in an equal 1:1 ratio, stratified by large versus small schools, into intervention or active control conditions. We will use block randomization with block sizes of 2, which will be stratified by large schools versus not, where large is ≥1000 students. We use block size of 2 because there are only 4 schools in this pilot trial. [name] (PI) will use Stata (ralloc command) to generate the randomization list, which will be entered into REDCap using the randomization module. Because this is a cluster randomized trial, we will randomize schools after they are determined to have met all the eligibility requirements and they officially enroll in the study. Upon school enrollment, a research assistant will be responsible for entering the school into the REDCap database and hitting the "randomize" button. Randomization will occur prior to school staff

screening/enrollment and prior to intervention delivery. We will conceal allocation from schools. This is an unblinded study. This is an educational intervention that cannot be blinded because study participants will be able to tell which condition they are in based on the content they receive. Unblinding could introduce bias, including social desirability bias, attrition bias, bias in intervention participation, and bias in reporting adverse events. Outcomes are assessed via self-reported online surveys, so there is no concern about bias about the blinding for outcome assessors.

PLANTS (Providing LGBTQ+ Adolescents with Nurturance, Trustworthiness, and Safety) intervention is an online-delivered training program, including asynchronous and synchronous activities. This intervention was informed by the Information-Motivation-Behavior theory to target skills, self-efficacy, knowledge, and outcome expectations. There are approximately 20 asynchronous online modules that cover a variety of topics including lessons on LGBTQ+ terminology, names and pronouns, resources, antibullying, gender neutral bathrooms, student confidentiality, active empathic listening, and school policies. Each module includes recorded presentations, student testimonials, activities, and downloadable resources for future reference. Every month, 7-9 lessons are opened. There are 2-3 synchronous group events delivered via Zoom that are 1.5 hours each.

The active control arm is an email-based intervention, EMAILS (E-learning to Maximize Academic Inclusion of LGBTQ+ Students), in which existing public resources for supporting, affirming, and protecting LGBTQ+ are emailed to participants. All of these resources are also provided to intervention participants. The topics of the email intervention are similar to those of PLANTS.

At the 4 enrolled schools, we will administer online surveys to all staff members (i.e., a census of teachers, administrators, nurses, counselors) via REDCap software. With staff emails provided by administrators, we will send staff a screening survey, consent form, and baseline survey. Subsequently, we will sample a subset of the intervention and control groups for individual interviews to explore implementation outcomes more deeply.

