#### 6.3 Measures to Minimize Bias: Randomization and Blinding

We will randomize schools in an equal 1:1 ratio, stratified by large versus small schools, into intervention or active control conditions. We will use permuted block allocation (with block size=2) to randomize schools to the intervention or active control conditions. We use block size of 2 because there are only 4 schools in this pilot trial. The permuted blocks will be created using the "ralloc" package for Stata. We will use REDCap's Randomization Module. We will randomize schools after they enroll in the study, but before school staff complete baseline surveys. [name] will create the randomization files in Stata, and the study coordinator will allocate schools to conditions in REDCap. We will conceal allocation from schools.

This is an unblinded study. This is an educational intervention that cannot be blinded because study participants will be able to tell which condition they are in based on the content they receive. Unblinding could introduce bias, including social desirability bias, attrition bias, bias in intervention participation, and bias in reporting adverse events. Outcomes are assessed via self-reported online surveys, so there is no concern about bias about the blinding for outcome assessors. We do not anticipate planned or unplanned breaking of randomization allocation to participants or schools.

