# 8 STUDY ASSESSMENTS AND PROCEDURES

#### 8.1 Endpoint and Other Non-Safety Assessments

School Screener

Version 1.0

2024.04.05

- 1. Inclusion/exclusion will be assessed over Qualtrics, the phone, Zoom, or in-person by study staff to school administrators. These are the exact questions:
  - a. Does your school plan to participate in the 2023 MetroWest Adolescent Health Survey?
  - b. Does your school plan to participate in the 2025 MetroWest Adolescent Health Survey?
  - c. Does your school grant us permission to access your MWAHS data?
  - d. Will your school provide emails addresses for all school staff so we can recruit them to the trial?
  - e. Will your school provide our team with a letter of support denoting their participation in our study?
- 2. Public school data: We will gather all publicly available data from the Massachusetts Department of Elementary and Secondary Education website, including school size.
- 3. Randomization: Upon enrollment of a school, we will randomize them to either PLANTS or EMAILS based on our stratified blocked randomization.

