#### 9.2 Sample Size Determination

#### Primary Endpoints

To adequately evaluate the primary endpoints, we need precise estimates of acceptability, appropriateness, and feasibility. We calculated our sample size based on our primary outcomes, a 5% error rate, and best practices for feasibility studies. The median number of teachers at each MetroWest Region high school is n=86. With 4 schools in our sample, we anticipate inviting a total  $\geq$ 344 school staff to participate in the pilot study. Assuming 50% agree to participate, 50% of participants are in the PLANTS study arm, and 75% of PLANTS participants complete the follow-up survey (reduced n=65), we can estimate 95% CI widths  $\leq$ 0.33 for AIM, IAM, and (based on the largest upper CI limit of the AIM, IAM, and FIM standard deviations) and  $\leq$ 10.1 for SUS. Such precision levels are sufficient.

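### Independent blocks of 2 within school-size strata deliver the promised 1:1 school allocation only if each stratum holds an even number of the four schools, and the plan does not say that it does

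*Combined protocol and SAP*

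**What the plan says.** Section 4.1 (Overall Design) sets the ratio and the strata: "We will randomize schools in an equal 1:1 ratio, stratified by large versus small schools, into intervention or active control conditions". It gives the method as "We will use block randomization with block sizes of 2, which will be stratified by large schools versus not", with large defined as at least 1000 students, and the reason as "We use block size of 2 because there are only 4 schools in this pilot trial". Section 6.3 restates it: "We will use permuted block allocation (with block size=2) to randomize schools to the intervention or active control conditions".

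On timing, Section 4.1 has a research assistant randomise in REDCap when a school enrols. Section 8.1 agrees: "Upon enrollment of a school, we will randomize them to either PLANTS or EMAILS based on our stratified blocked randomization".

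The school criteria in Sections 5.1 and 5.2 contain no size requirement. No section says how many of the four schools are large, or what to do with a half-used block.

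Section 9.2 sizes the primary endpoints on the assumption that "50% of participants are in the PLANTS study arm", which leads to 65 PLANTS completers and 95% interval widths of at most 0.33 (AIM, IAM, FIM) and 10.1 (SUS).

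**The concern.** A block of 2 balances the arms only when both of its places are used. Two strata with separate lists and four schools in all can leave one half-used block in each stratum, and nothing in the plan ties those two blocks together. The plan can then be followed exactly and still miss its own 1:1 ratio.

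A 3:1 split touches several planned analyses. If PLANTS is the arm with one school:
- the primary sample is about half the planned size;
- the within-PLANTS pre-post models in Section 9.4.3 have no second school from which to estimate the school random effect and intraclass correlation, and their school-size term is constant;
- the primary-endpoint subgroup models in Section 9.4.7, which adjust for school clustering, meet the same problem.

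If EMAILS is the arm with one school, the comparator has no school-level replication. Either way, the arm-specific percentage of schools with adverse events (Section 9.4.4) can only be 0% or 100% in the single-school arm.

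**Working it through.** **Inputs.** Four schools; blocks of 2; two strata with independent lists (Sections 4.1, 6.3). A median of 86 teachers per school, 50% participation, 50% of participants in PLANTS, 75% follow-up, widths 0.33 and 10.1 (Section 9.2). The size mix is not given.

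**The plan's own sample size.** 4 × 86 = 344 invited; 344 × 0.50 × 0.50 × 0.75 = 64.5, stated as 65. This reproduces.

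**Allocation by size mix (exact enumeration).**

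| Schools in the two strata | PLANTS has 1 | PLANTS has 2 | PLANTS has 3 | P(3:1 either way) |
|---|---|---|---|---|
| 2+2, 4+0 or 0+4 | 0 | 1 | 0 | 0 |
| 3+1 or 1+3 | 1/4 | 1/2 | 1/4 | 1/2 |

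In a 3+1 mix, the first two schools of the three-school stratum go one to each arm. The third opens a new block and goes to either arm with probability 1/2. The lone school in the other stratum also opens a block, independently, with probability 1/2. The two land in the same arm with probability 1/2, which gives 3:1. A 4:0 split cannot occur.

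**Overall probability (assumption: each school is independently large with probability p).** P(3+1 mix, either way round) = 4p³(1−p) + 4p(1−p)³. P(3:1) is half of that, 2p(1−p)[p² + (1−p)²].
- p = 0.1 or 0.9: 2 × 0.09 × 0.82 = 0.148
- p = 0.3 or 0.7: 2 × 0.21 × 0.58 = 0.244
- p = 0.5: 2 × 0.25 × 0.50 = 0.25, the maximum

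PLANTS is the single-school arm in half of these cases: about 0.07 to 0.125.

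**Primary precision (assumption: about 86 staff in every school).** Standard deviations implied by the stated widths at n = 65, from SD = (width/2) × √65 / t(0.975, 64): 0.666 for AIM, IAM and FIM, and 20.4 for SUS. New width = 2 × t(0.975, n−1) × SD / √n, before clustering.

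| PLANTS schools | Completers | AIM/IAM/FIM width | SUS width |
|---|---|---|---|
| 1 | 86 × 0.50 × 0.75 = 32.25, about 32 | 0.48 | 14.7 |
| 2 (plan) | 64.5, stated as 65 | 0.33 | 10.1 |
| 3 | 96.75, about 97 | 0.27 | 8.2 |

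**Between-arm comparison.** For equal-sized schools with a common between-school variance and no covariates, the variance factor is 1/2 + 1/2 = 1 under 2:2 and 1 + 1/3 = 1.33 under 3:1. The between-school standard error rises by √1.33 = 1.15, about 15%. This leaves out the school-size term of the planned model.

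**The case against.** The strongest reply is that the hazard rests on a fact the documents omit. School size is public and is gathered at the school screener (Section 8.1), so the investigators may know the mix when they build the list. If it is 2+2 or all of one size, the scheme always gives 2:2. That stands: the 50% applies to a 3+1 mix only, and a reader who took it as the overall risk would be going beyond the documents.

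Three other strong readings also fail.
- A reader might blame the school-by-school timing. Randomising all four schools on one day from the same stratum lists gives the same 50%. The cause is odd strata with independent blocks.
- A reader might conclude that 3:1 makes arm and school inseparable and the comparison newly impossible. An unadjusted comparison has 4 − 2 = 2 between-school degrees of freedom under either split. The loss is about 15% in the between-school standard error, on a comparison that four schools already make weak and that is a secondary objective of a pilot.
- A reader might take any 3:1 split as harm to the primary endpoint. That endpoint is descriptive and uses PLANTS participants only (Sections 9.3, 9.4.2). It suffers only when PLANTS has the single school; the equally likely reverse gives about 97 completers and narrower nominal intervals.

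The figure of 32 also assumes equal schools. After a 3:1 split the single school always comes from the three-school stratum, so its staff may well be more than 86 if that stratum is large, or fewer if it is small.

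What the reply does not remove is the gap between promise and method: no section states the mix, and none covers an incomplete block.

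**Conclusion.** The point holds as a conditional one. The scheme guarantees the stated 1:1 school allocation only for even strata, and the documents do not show that the strata are even. Given a 3+1 mix the chance of 3:1 is exactly 0.50, split equally between the arms. Without the mix it is about 0.15 to 0.25, with about 0.07 to 0.125 for a single PLANTS school, if schools are independently large with probability 0.1 to 0.9.

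The widths of about 0.48 and 14.7 rest on equal schools of about 86 staff, on standard deviations back-calculated from the plan's own widths, and on no clustering. In that case the within-PLANTS school variance and intraclass correlation also cannot be estimated. The change is worth making because the risk can be removed at little cost; the documents do not support a claim that the trial is likely to be unbalanced.

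**What to change.** In Sections 4.1, 6.3 and 8.1, replace the independent stratum lists with one restricted draw, made after all four schools have enrolled, that permits only 2:2 allocations. One way is to rank the schools by the public size data, pair the two larger and the two smaller, and randomise within each pair.

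The cost is protocol wording, a new allocation list and a wait for the first schools until the fourth has enrolled. With a 3+1 mix the pairs will not follow the 1000-student cut. The change secures two schools per arm; it does not secure exactly 50% of participants, since schools differ in size and uptake.

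If the size mix is already known to be even, state it, and the present scheme can stay. If allocation has already taken place, report the size mix and the split, and restate the precision in Section 9.2 if the split is not 2:2.

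### Randomising four schools one at a time in fixed blocks of 2 lets the study team deduce one or two of the four allocations before the school enrols; a single draw after all four have enrolled would prevent this

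*Combined protocol and SAP*

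**What the plan says.** **Scheme.** Section 4.1 states: "We will randomize schools in an equal 1:1 ratio, stratified by large versus small schools", with large meaning at least 1000 students. The block size is fixed: "We will use block randomization with block sizes of 2, which will be stratified by large schools versus not". The reason given is: "We use block size of 2 because there are only 4 schools in this pilot trial". Section 6.3 repeats it: "We will use permuted block allocation (with block size=2) to randomize schools to the intervention or active control conditions".

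**Timing.** In 4.1 the step follows each school's enrolment: "Upon school enrollment, a research assistant will be responsible for entering the school into the REDCap database" and for then triggering the randomisation. Item 3 of the School Screener in 8.1 reads the same way: "Upon enrollment of a school, we will randomize them to either PLANTS or EMAILS based on our stratified blocked randomization". Section 6.3 places randomisation after school enrolment and before the staff baseline surveys. It does not say to wait until all four schools have enrolled.

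**Roles.** Section 4.1 has the principal investigator generate the list in Stata and a research assistant perform the allocation. Section 6.3 says that the person making the list "will create the randomization files in Stata, and the study coordinator will allocate schools to conditions in REDCap". The two sections therefore give the allocation step to different roles.

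**Concealment.** Sections 4.1 and 6.3 both say that allocation is concealed from schools and that the trial is unblinded. Neither says that the list, the block size or earlier allocations are withheld from the study team, or that someone independent of enrolment holds the list.

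**The concern.** Concealment has two sides. Randomising a school only after it is eligible and enrolled stops that school, or the team, from backing out once its arm is shown. It does not stop the team from anticipating the next arm while deciding which school to approach or finalise next. A fixed block of 2 in an open trial is the most predictable blocked scheme available, and the block size is printed in the protocol.

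Four schools make each allocation count. The four primary endpoints are PLANTS-arm means compared with benchmarks (sections 9.1 and 9.4.2), so the receptiveness of the PLANTS schools enters them directly. Section 2.3.3 itself links a school's agreement to take part with leadership that favours supporting these students, so school attitude is a plausible driver of the ratings. If a more receptive school were placed in a slot known to be PLANTS, the primary means and the PLANTS-versus-EMAILS contrast could both shift. Section 9.4.3 plans to adjust for baseline imbalances in secondary models, but with four clusters that cannot be relied on to repair such a shift. Sections 4.1 and 6.3 list biases that could follow from the lack of blinding; selection through predictable allocation is not among them.

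**Working it through.** The plan states no figure for predictability, so there is none to reproduce.

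**Inputs.** Four schools, 1:1 ratio, fixed blocks of 2, two size strata (4.1 and 6.3); randomisation on each school's enrolment (4.1 and 8.1, School Screener item 3). The numbers of large (L) and small (S) schools are not given, so every split with L + S = 4 is shown.

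**Step 1: allocations fixed in advance.** The second school in each block of 2 must receive the arm that the first did not. The number determined is D = floor(L/2) + floor(S/2).

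**Step 2: expected correct guesses.** A team that uses the determined slots and guesses the rest at even odds expects G = D + (4 − D)/2 correct. Pure chance gives 4 × 0.5 = 2.0.

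| Size split | D | G |
|---|---|---|
| 4/0 or 0/4 | 2 + 0 = 2 of 4 (50%) | 2 + 2/2 = 3.0 |
| 2/2 | 1 + 1 = 2 of 4 (50%) | 2 + 2/2 = 3.0 |
| 3/1 or 1/3 | 1 + 0 = 1 of 4 (25%) | 1 + 3/2 = 2.5 |

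**Step 3: the list holder.** Anyone with sight of the ordered list can read the next slot in each stratum. That amounts to 4 of 4 only if the person also follows each school's stratum and order of enrolment.

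**Step 4: weight of one school.** Section 9.2 expects 344 invited × 0.50 × 0.50 × 0.75 = 64.5, which it rounds to 65 PLANTS follow-up surveys. If two PLANTS schools contribute equally (an assumption), each supplies about 65/2, or 32, which is half of the primary data.

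**Step 5: balance under the present scheme.** With a 3/1 split, the stratum of three has one complete block (one school per arm) plus one school from an unfinished block, and the other stratum has a single school. The number of PLANTS schools is 1 plus two independent even-odds draws: 1 with probability 0.25, 2 with probability 0.50, 3 with probability 0.25. A 3:1 imbalance in one direction or the other therefore has probability 0.50. The other splits always give 2:2.

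**Step 6: after the change.** If no draw exists until all four schools have enrolled, no allocation can be known before enrolment, so D = 0 for the team and for the person making the draw. Restricting to 2:2 while respecting strata leaves 2 × 2 = 4 allocations for a 2/2 split. For a 4/0 split it leaves 6 (choose 2 of 4). For a 3/1 split it also leaves 6: 3 with the single school in PLANTS and 3 with it in EMAILS.

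**The case against.** The best case for the plan has four parts.

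- **Safeguards exist.** Schools are randomised only after eligibility and official enrolment, the list sits in REDCap's randomisation module, and a different person from its author performs the allocation. This stands as protection against dropping a school once its own arm is known. It does not make the second slot of a block of 2 unpredictable, nor hide the list from its author.
- **Discretion is undocumented.** Steering needs a choice among candidate schools or over their order. The school criteria in 5.1 are largely factual or decided by the school, and 5.2 has no school exclusions. The documents give neither the number of candidate schools nor who recruits them. A section on key roles and governance is listed in the table of contents but is not in the text available for review, so nothing can be inferred from its absence. This point stands and limits the finding to an opportunity for selection.
- **The size of any bias is unknown.** This also stands. The primary analysis is descriptive, the arm contrast is secondary, and all schools are volunteers.
- **The remedy is partial.** Staff are screened and consented after their school has been allocated, in an unblinded trial. That separate route to selection remains open whichever way schools are randomised.

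A reader might also infer that school-by-school randomisation makes the arms run at different times of the school year. The documents do not support that. Section 4.1 says only that randomisation precedes staff screening and delivery, no passage starts delivery when a school is randomised, and 6.1.1 gives EMAILS a duration and pace similar to PLANTS.

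**Conclusion.** The weakness is real and modest. As 4.1 and item 3 of the School Screener are written, 1 of 4 allocations (3/1 size split) or 2 of 4 (2/2 or 4/0 split) can be deduced before the school enrols, and a holder of the list can read the next slot in either stratum. This rests on reading those sections as school-by-school randomisation, which is their plain sense, and on the team being aware of the printed block size and of earlier arms.

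Two stronger readings should be resisted. One is that the team already knows the arms, or that the principal investigator knows all four. The text supports only that they could be deduced, and for all four only by tracking stratum and enrolment order. The other is that schools have been or will be steered. Nothing shows this, and its effect on the endpoints cannot be sized from the documents. The case for change is that the opening can be closed at very little cost.

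**What to change.** 1. Complete enrolment of all four schools, with eligibility confirmed and letters of support received, before any allocation is generated.
2. Randomise all four in one step by a single draw, with the seed recorded, from the allocations that respect the size strata and give two schools per arm.
3. Replace the school-by-school wording in 4.1 and in School Screener item 3 of 8.1, and revise 6.3 to describe the single draw in place of sequential blocks.
4. Reconcile 4.1 and 6.3 on whether the research assistant or the study coordinator performs the allocation.

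**Cost.** Protocol wording, with no extra schools or staff. The first schools to enrol wait until the fourth has done so, and that wait must fit within the estimated 12-month study duration in the synopsis. The restriction to 2:2 also removes the 0.50 probability of a 3:1 imbalance that the present scheme carries under a 3/1 size split.
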